The development of resistance and the utilization of RPV-containing products according to the products' SmPC will be assessed through a drug utilization study (DUS) conducted in HIV observational cohorts within Europe. Additionally, the DUS will provide context to the observed rates of virologic failure and development of resistance for patients initiating RPV treatment by describing the treatment outcomes of patients initiating efavirenz (EFV). The relative risk of virologic failure and resistant-associated mutations (RAMs) after initiating RPV-containing regimens will be estimated separately by comparing the incidence rates of virologic failure and RAMs among RPV-treated patients to the incidence of virologic failure and RAMs among EFV-treated patients. For all study objectives, frequency and rates will be reported for the RPV and EFV-treated groups separately, as well as for RPV relative to EFV.

The objectives of the DUS are to describe the following in the context of routine clinical practice:

Primary objectives:

- To describe the proportion of patients treated with RPV in accordance with the SmPC The proportion of patients treated with RPV in accordance with the SmPC will be described by estimating a proportion separately for each recommendation of patient treatment. The denominator for each proportion will consist of the number of all patients initiating RPVcontaining regimens included in the study. Proportions will be estimated separately using the following numerators:
 - o The number of patients naïve to HIV treatment regimens
 - o The number of patients with documented pre-treatment screening for ARV RAMs
 - The number of patients initiating RPV-containing regimens with a baseline viral load \leq 100,000 HIV-1 ribonucleic acid (RNA) copies/mL
- To describe treatment emergent RAMs in patients treated with RPV or EFV-containing regimens
- To describe virologic failure in patients treated with RPV or EFV-containing regimens

Secondary objectives:

- To describe the demographic characteristics, comorbidities, and medical condition of patients initiating RPV or EFV treatment
- To describe antiretroviral (ARV) treatment status (naïve/experienced) of patients prior to initiating RPV or EFV treatment
- To describe prior use of ARV treatment, if any, of patients initiating RPV or EFV-containing regimens
- To describe the frequency of pre-treatment RAMs for RPV and EFV among patients subsequently initiating RPV or EFV treatment respectively
- To describe viral load at start of RPV or EFV treatment
- To describe viral load over the course of RPV or EFV treatment

- To describe HIV-treatment regimens and concomitant medications of patients initiating RPV or EFV-containing regimens
- To describe changes in HIV treatment and concomitant medication over the course of RPV and EFV treatment
- To describe reasons for switch of ARV treatment
- To describe adverse events over the course of RPV or EFV treatment

A DUS of HIV-positive patients captured in existing European cohorts initiating RPV treatment will be used to meet the study objectives. HIV cohorts provide detailed longitudinal information on patient demographics, HIV treatment regimens, treatment status (naïve/experienced), duration of therapy, clinical events, reason for discontinuation of HIV treatment, and adverse events. HIV cohorts included in the study will be determined by a feasibility assessment to evaluate the granularity of assessment of HIV resistance and variables needed to assess the use of RPV-containing products in accordance with the products' SmPC.

Additionally, a comparator cohort of EFV-treated patients will be included to provide contemporary context to utilization and outcomes observed within the RPV-treated group. The EFV treatment group will further elucidate which patient characteristics are more likely to influence health-care providers to channel patients to EFV or RPV containing regimens. Additionally, the EFV-treatment group will provide a better understanding of the observed rates of virologic failure, resistance patterns, and prescribing factors observed within the RPV-treatment group.

The DUS will identify a minimum of 600 patients newly initiating RPV-containing regimens and 600 patients newly initiating EFV-containing regimens and captured in one or more of the HIV cohorts currently established in Europe. Exposure to RPV-containing regimens will be measured by the presence of prescription records for the fixed dose combination (FDC) of RPV with emtricitabine/tenofovir (TRUVADA TM (Gilead)) or single agent tablets of RPV among the patient data. Exposure to EFV will be measured by the prescription records for the available formulations of EFV in patient data. Information on drug use, including dispensing date, dose prescribed, quantity dispensed and the length of drug supply, will also be captured from the prescription records in the cohort database. The sample size targets will produce an error rate of no more than 5% for the proportions estimated. A minimum of 600 RPV-treated patients will be included in the DUS to assess the proportion of appropriate use of RPV-containing regimens. The study period will start at the date of market availability of RPV-containing products in the participating counties and will end when in total 600 patients from each treatment group have been included in the study and followed for 12 months, until virologic failure, or lost to follow-up, whichever occurs first.

An evaluation of appropriate use will be conducted through an analysis describing and summarizing the prescribing patterns and use of RPV-containing products. The prescriptions will be summarized by patient demographics (age, sex, geography) and clinical characteristics (comorbidities and concomitant medications). In addition, the details of RPV-containing regimens use patterns will be described, including duration of use, persistence of therapy, and usage of other HIV treatments. This analysis will describe and summarize the utilization patterns of RPV-containing regimens with respect to viral load, CD4 counts, pretreatment resistance testing, HIV treatment status (naïve/experienced), prior HIV treatment regimens, concomitant medications, and comorbidities. The analysis will ascertain the number of patients initiating treatment with RPV-containing regimens and the proportion of patients treated in accordance with the RPV SmPC. Proper prescribing will be summarized by patient demographics and potential confounders. Incidence rates of virologic failure, pre-treatment resistance, and treatment-emergent resistance will be calculated for the RPV and EFV-treated patients, separately. The three primary event rates of interest (incidence rates of virologic failure, pre-treatment resistance, and treatment-emergent resistance) will be analyzed in 3 separate sets of analyses. Additional descriptive analyses will include incidence rates for each drug calculated by dividing the number of events by the total person-exposure time and expressed as the number of events per person-year, and 95% confidence intervals.

Relative risks comparing the RPV-containing regimens with EFV-containing regimens and 95% confidence intervals will be calculated and appropriate stratified analyses will be conducted for virologic failure and emergence of treatment resistance. Poisson regression models will be used to adjust for the appropriate

factors that influence the risk of virologic failure and treatment-emergent resistance. Adjustments for imbalances between the treatment groups before receiving the first dose of RPV or EFV-containing regimens will be applied using accepted methods based on sample size availability and the observed overlap of key patient characteristics based on propensity score construction.

Given the recognized limitations of assessing food intake and treatment adherence in large observational studies conducted over several months, the feasibility of collecting food intake and treatment adherence data within the cohorts will be further explored. Currently, the HIV cohorts do not routinely collect data on ARV treatment adherence or pill intake with food. Optimally, HIV cohort data collection protocols will be modified for all RPV-treated patients to facilitate data collection on both ARV treatment adherence and pill intake with food at each patient visit. Under this scenario these measures will be added to the analysis described above. A nested case-control study will be conducted to address the CHMP's concerns on the effects of food intake on virologic failure among patient treated with RPV, while also evaluating ARV treatment adherence. The objective of the nested case-control analysis is to quantify the risk of virologic failure associated with adherence to ARV treatment and dietary instructions. Patients who experience virologic failure while under observation in the DUS will be selected into the study as cases. Patients who do not experience virologic failure while under observation and have similar experience with known confounders for virologic failure will be matched to cases using the incidence-density sampling method. This subgroup of patients from the DUS will be contacted and have their ARV treatment adherence and pill intake with food assessed through a one-time questionnaire assessing both adherence parameters over the past seven days. The methodology for the nested case-control study is provided in parallel with the DUS in this protocol.

ABBREVIATIONS

AACTG	Adult AIDS Clinical Trials Group
ARCA	Antiretroviral Resistance Cohort Analysis database
ARV	antiretroviral
BMI	body mass index
CHIC	Collaborative HIV cohort
CHMP	The Committee for Medicinal Products for Human Use
CI	confidence interval
CoRIS	Cohort of Spanish AIDS Research Network
DUS	Drug Utilization Study
EFV	efavirenz
FDC	Fixed dose combination
FTC	emtricitabine
FHDH	French Hospital Database on HIV
GPP	Good Pharmacoepidemiology Practice
HAART	highly active antiretroviral therapy
HIV-1	human immunodeficiency virus type 1
IRB	Institutional Review Board
J&JPRD	Johnson & Johnson Pharmaceutical Research and Development LLC.
MAR	missing at random
MCAR	missing completely at random
MNAR	missing not at random
M-PEMS	Modified Prescription Event Monitoring Study
NNRTI	non-nucleoside reverse transcriptase inhibitor
NVP	nevirapine
OR	Odds ratio
PI	protease inhibitor
PSUR	Periodic Safety Update Report
RAM	resistance associated mutation
RMP	Risk Management Plan
RNA	ribonucleic acid
RPV	rilpivirine
SD	standard deviation
SERAD	Self-Reported Adherence
SHCS	Swiss HIV Cohort Study
SHCS-AQ	Swiss HIV Cohort Study Adherence Questionnaire
SMAQ	simplified medication adherence questionnaire
SmPC	Summary of Product Characteristics
STROBE	The Strengthening the Reporting of Observational Studies in Epidemiology
TDF	tenofovir disoproxil fumarate
TDR	transmitted drug resistance
VAS	visual analog scale

1. INTRODUCTION

1.1. Background

Rilpivirine (RPV) is an NNRTI for the treatment of HIV-1 infection in antiretroviral treatment-naïve adult patients with a baseline viral load \leq 100,000 HIV-1 RNA copies/mL. RPV will be available as two formulations on the European market: a single agent, marketed by Janssen-Cilag International NV, and a fixed-dose combination containing FTC/RPV/TDF, marketed by Gilead Sciences International Ltd. The CHMP has requested further assessment of the development of resistance and whether the product is used in accordance with the Summary of Product Characteristics (SmPC). The development of resistance and the utilization of RPV according to the SmPC will be assessed through a drug utilization study (DUS) conducted in HIV observational cohorts within Europe. Additionally, the DUS will provide context to the observed rates of virologic failure and development of resistance by describing the treatment outcomes of patients treated with efavirenz (EFV). The relative risk of virologic failure and resistantassociated mutations (RAMs) after initiating RPV-containing regimens will be estimated separately by comparing the incidence rates of virologic failure and RAMs among RPVtreated patients to the incidence of virologic failure and RAMs among EFV-treated patients.

Several factors have been shown to be associated with virological response to antiretrovirals (ARV) for the treatment of HIV-1, including the degree of immunodeficiency and level of plasma HIV RNA when therapy is initiated, antiretroviral experience, drug resistance, and type of and adherence to the therapeutic regimen (Hull, 2009).

Virological response to highly active antiretroviral therapy (HAART) regimens has been evaluated among patients enrolled in large, observational HIV cohorts. These studies have included evaluations of NNRTI and protease inhibitor (PI)-containing regimens (Paredes, 2000; Cozzi-Lepri, 2002) as well as short term and long term virological response when treated with NNRTI or PI-based HAART regimens (Mocroft, 2006). A few cohort studies have specifically examined virological failure among patients initiating nevirapine (NVP)-containing regimens or EFV-containing regimens. Phillips and colleagues conducted a study among 2203 patients in EuroSIDA who began a regimen with nevirapine or efavirenz after July 1997 (Phillips, 2001). A total of 1325 patients initiated NVP and 878 EFV. During a median of 8 months follow-up, 669 patients experienced virological failure giving an overall rate of 0.48 per year (0.83 per year if excluding those in first 6 months of follow-up who had baseline viral load >500

copies/ml). A total of 505 people on a NVP regimen experienced virological failure compared with 164 people on an EFV regimen, giving incidence rates of 0.55 per personyear and 0.35, respectively. A more recent EuroSIDA analysis examined virological outcome and drug resistance in 759 patients starting NNRTI-containing regimens (Bannister, 2008). A total of 287 (78.3%) of the 389 NVP patients and 168 (45.4%) of the 370 EFV patients experienced virological failure. NNRTI-resistant HIV was detected in 3% of patients at baseline. Out of the 131 patients still on an NNRTI and with resistance test results available at time of virological failure, NNRTI resistance was detected in 86% of patients and was similar between groups. The high levels of NNRTI resistance suggest that these drugs fostered selection pressure, and that patients had actually adhered to their regimens.

Several large HIV cohort databases have investigated the prevalence of transmitted drug resistance (TDR). Among 525 chronically infected treatment-naïve patients in the EuroSIDA cohort, the overall prevalence of TDR was 11.4% from 1996-2004 (Bannister, 2008). In the German HIV-1 Seroconverter cohort of 1276 patients, the overall prevalence of TDR was 12.4% from 1997 through 2007. NRTI associated resistance was identified most frequently (6.3%), followed by NNRTI resistance (2.4%) and PI resistance (2.1%) (Bartmeyer, 2010). In the Swiss HIV cohort of 822 newly infected patients identified from 1996-2005, the overall prevalence of TDR was 7.7% for any ARV drug, 5.5% for NRTIs, 1.9% for NNRTIs, and 2.7% for PIs (Yerly, 2007). A recent investigation by the UK Collaborative Group in HIV drug resistance reported a decline in the rate of TDR in treatment-naïve recently and chronically infected patients from around 14% in 2001-2002 to around 8% by the end of 2004 (Dunn, 2007).

The level of adherence to antiretroviral therapy (ART) is one of the critical factors in achieving viral suppression, avoiding viral rebound, increasing CD4 cell counts, and minimizing the risk of development of AIDS-defined illnesses that may result in death among HIV-infected patients on ART (Cambiano, 2010). Patient self-reports via questionnaires or interviews is the most frequently used measure of treatment adherence to HAART. More quantitative measures exists, such as electronic monitoring devices, pill counts, and pharmacy prescription refill monitoring; however use of these methods is limited by high cost, labor intensity, and other issues (Nieuwkerk and Oort, 2005). Self-report questionnaires that have been used in the clinical setting and validated include the simplified medication adherence questionnaire (SMAQ), the visual analog scale (VAS), the Adult AIDS Clinical Trials Group (AACTG) questionnaire, and the Self-Reported Adherence (SERAD) (Deschamps, 2008). While self-reports offer significant correlation

with viral load, this measurement method tends to underestimate nonadherence. An adherence questionnaire (SHCS-AQ) was introduced into follow-up of the Swiss HIV Cohort Study (SHCS) in July 2003 to assess overall doses missed and drug holidays over the past 4 weeks. The SHCS-AQ has been validated in a small study that compared the European HIV treatment questionnaire, a visual analog scale, and electronic monitoring. Using virological failure as the gold standard, the SHCS adherence questionnaire in the validation study performed slightly better than either electronic monitoring or a combination of the SHCS-AQ and a VAS with a sensitivity of 88% and a specificity of 79% (Deschamps, 2008). Despite its importance, there are no readily available measures of treatment failure ordinarily used in routine clinical practice, nor are there methods available for comparison of adherence levels across large patient populations captured in the multiple HIV cohorts.

Patient adherence to food requirements also affects optimal bioavailability of the RPV regimen and is a component of adherence to the SmPC. The Sponsor have evaluated methods of adherence measurements of dietary intake (weighing and measuring of food, 24-hour recall, and food diaries) considered to have reliable face validity, content validity, construct validity, and reliability (Vitolins, 2000). Assessment of patient adherence to the RPV-containing products' SmPC would require careful measurement that is not practical within large observational studies such as modified prescription event monitoring studies (M-PEMS) or DUS. Traditionally, clinical studies designed to measure dietary adherence have involved weighing and measuring all food and drinks consumed. Such labor-intensive methods are impractical within an M-PEMS or DUS due to both frequency of the required measures and length of follow up proposed in the Another method for measuring dietary adherence is 24-hour recall, where studies. patients are asked to recall food intake during the previous day. Interviews are typically conducted by trained interviewers or nutritionists. Although this method is less complex than weighing and measuring it is not practical for measuring dietary adherence in large groups included in M-PEMS or DUS due to the high variability of diet day to day and the required frequency of patient interviews. Dietary records or food diaries are also used to measure food adherence. These are detailed records of the types and quantities of food and beverages consumed during a specified period. The specified period is usually 3-7 days. This method puts considerable burden on the patient, particularly over the anticipated course of rilpivirine therapy, and is not practical within an M-PEMS or DUS.

Given the recognized limitations of assessing food intake and treatment adherence in large observational studies conducted over several months, the feasibility of collecting food intake and treatment adherence data within the cohorts will be further explored. Options to be explored will include using one of the accepted methods of measuring ARV treatment adherence and pill intake with food in a smaller sample of patients within the HIV cohorts.

In summary, a DUS (using data from multiple existing HIV cohorts in Europe) will be conducted in order to address the CHMP concerns on the potential for development of virologic resistance and potential for improper prescribing or use (according to the SmPC). HIV cohorts have a demonstrated history of assessing virologic failure, RAMs, and associated risk factors. This DUS will provide significant real-world data on (amongst other parameters) ARV drug resistance, frequency of resistance testing, viral load at the start of treatment, prior use of ARV treatment, reasons for switch of ARV treatment, adverse events, concomitant medications and comorbidities. Currently, the HIV cohorts do not routinely collect data on ARV pill adherence or pill intake with food. The feasibility of collecting data on ARV treatment adherence and pill intake with food within the HIV cohorts for each patient at each visit will be assessed. Additionally, a nested case-control study will be conducted to assess the effects of ARV treatment adherence and pill intake with food on the risk of virologic failure with RPV will be assessed. As the nested case-control analysis will assess a smaller sample of RPV-treated patients that have already been identified as part of the DUS, details on the study design are included in this protocol.

1.2. Overall Rationale for the Study

The CHMP has requested an assessment of the use of RPV-containing products by prescribers as well as patients in accordance with the SmPC. The development of resistance and the utilization of RPV-containing products according to the products' SmPC will be assessed through a drug utilization study (DUS) conducted in HIV observational cohorts within Europe. HIV cohorts included in the study will be determined by a feasibility assessment to evaluate the granularity of collection of HIV resistance data and of the variables necessary to assess the proper use of RPV in accordance with the products' SmPC.

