2. OVERVIEW OF STUDY DESIGN

2.1. Study Design

This DUS will be implemented in one or more large HIV cohorts established in Europe. Data will be collected longitudinally and recorded in the HIV cohorts' databases. A minimum of six hundred patients will be entered into the study based on the prescribing of RPV-containing regimens, either as a single agent or as a FDC. An additional minimal number of 600 patients will be entered into the study based on the prescribing of EFV-containing regimens. Retrospective data available in the HIV cohorts will be used to describe patient clinical characteristics prior to receipt of RPV-containing regimens.

Data will be collected in an observational manner such that the management of the patient is determined by the patient and the caregiver and not influenced by the DUS protocol. The DUS will evaluate care as it is provided. It will capture data on a heterogeneous population treated with RPV-containing regimens or EFV-containing regimens in a comprehensive manner without exclusions to assure representativeness of the populations treated with RPV or EFV-containing regimens.

All patients initiating RPV treatment will be eligible for inclusion in the DUS. Patients initiating EFV treatment will also be eligible for inclusion in the comparator group based on the date of EFV treatment initiation. Relevant IRB/EC and HA approvals will be secured prior to initiating the study.

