European HIV cohorts capture care as given and are generalizable to the population likely to be exposed to RPV-containing regimens. The proposed design does not interfere with the physician's decision regarding what to prescribe for the individual patient. Patients receive the drug in everyday practice and are not a highly selected group of patients who may not be representative of the 'real-world' population. The use of multiple cohorts located in several different countries increases the generalizability of the observed rates of use by physicians. The major strength of using the HIV cohorts for a DUS is the protocols for data collection have been specifically designed for HIV research (www.hicdep.com). Data are systematically collected on all clinical aspects salient to HIV care. These data include laboratory variables for HIV viral load, CD4+ counts, drug resistance information, concomitant medications, adverse events, and detailed information on HIV treatment. Additionally, patients are followed in the cohort until death or loss to follow-up from the cohort. Data are collected independent of the proposed DUS and are not subject to physician recall or potential biases involving selfreported drug prescribing or patient management. These data are collected longitudinally and in a time-dependent manner so that variation in time-dependent variables can be assessed. This is particularly important when considering the outcome of virologic failure and potential factors contributing to loss of virologic control. Finally, these data are collected electronically and do not place additional burden on the treating physician or patient.

Additionally, a comparator group of EFV-treated patients will be included in this study to provide contemporary context to utilization and outcomes observed within the RPVtreated group. The EFV-treated group will provide insight into patient characteristics DATE (6 September 2011)

likely to influence health-care providers to channel patients to EFV-containing regimens or to RPV-containing regimens. Additionally, the EFV treatment group will provide a better understanding of the observed rates of virologic failure and prescribing factors observed within the RPV-treated group.

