3.1.3. Data Source(s)3.1.3.1. Feasibility Assessment of European databases

An evaluation will be conducted of the following available HIV cohorts in Europe for their suitability for meeting the study objectives:

- EuroSIDA
- UK Collaborative HIV cohort (CHIC), with linkage to the UK HIV drug resistance database and the UK Register of HIV Seroconverters
- Danish HIV cohort
- German HIV-1 Seroconverter cohort
- Italian Antiretroviral Resistance Cohort Analysis database (ARCA)
- French Hospital Database on HIV (FHDH)
- Cohort of Spanish AIDS Research Network (CoRIS)

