4.5.2. Analysis of Appropriate Use

This analysis will describe and summarize the prescribing of RPV and EFV-containing regimens. The analysis will ascertain the number of patients exposed to RPV-containing regimens and EFV-containing regimens. The prescriptions will be summarized by patient demographics (age, sex, geography) and clinical characteristics (comorbidities and concomitant medications). In addition, the details of RPV and EFV-containing regimens use patterns will be described including duration of use, persistence of therapy, and usage of other HIV treatments.

This analysis will describe and summarize the utilization patterns of RPV-containing regimens and EFV-containing regimens with respect to viral load, CD4 counts, pretreatment RPV-containing regimens resistance testing, adverse events, HIV treatment status (naïve/experienced), prior HIV treatment regimens, concomitant medications, comorbidities, and route of infection. The analysis will ascertain the number of patients initiating RPV-containing regimens and the proportion of patients treated in accordance with RPV products' SmPC. Proportions will be estimated separately for each recommendation of patient treatment. The denominator for each proportion will consist of the number of all patients initiating RPV-containing regimens included in the study. Proportions will be estimated separately using the following numerators:

- The number of patients naïve to HIV treatment regimens
- The number of patients with documented pre-treatment screening for ARV RAMs

• The number of patients initiating RPV-containing regimens with a baseline viral load ≤ 100,000 HIV-1 ribonucleic acid (RNA) copies/mL

Proper prescribing will be summarized by patient demographics and potential confounders.

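### If a selected cohort enrols patients through a resistance test, the pooled proportion with pre-treatment resistance screening may be biased upward, and the plan has no step that would show it

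*Protocol*

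**What the plan says.** Section 1.2 makes source selection depend on a feasibility assessment with two parts. The first is that "HIV cohorts included in the study will be determined by a feasibility assessment to evaluate the granularity of collection of HIV resistance data". The sentence continues: "and of the variables necessary to assess the proper use of RPV in accordance with the products' SmPC". The Synopsis has a similar two-part criterion.

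Section 3.1.3.1 lists seven candidates and introduces them thus: "An evaluation will be conducted of the following available HIV cohorts in Europe for their suitability for meeting the study objectives". They are not yet selected. One is the "Italian Antiretroviral Resistance Cohort Analysis database (ARCA"). Another is the "UK Collaborative HIV cohort (CHIC), with linkage to the UK HIV drug resistance database". Section 2.1 leaves the number of sources open: "This DUS will be implemented in one or more large HIV cohorts established in Europe". Section 3.1.1 requires documented enrolment in the cohort before RPV or efavirenz treatment starts.

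Sections 1.3.1 and 4.5.2 define three primary SmPC proportions, each over all RPV starters included. One numerator is "The number of patients with documented pre-treatment screening for ARV RAMs".

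Section 2.2 asserts that "European HIV cohorts capture care as given and are generalizable to the population likely to be exposed to RPV-containing regimens". Section 5 lists the study's limitations and does not mention that sources are chosen partly on their resistance data. Section 4.5.2 summarizes proper prescribing by patient demographics, among which it counts geography. It states no result by cohort.

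**The concern.** Resistance data matter to this study in two ways. For treatment-emergent mutations, a source that records them in detail is simply a better source. For the screening proportion, the presence of a test is itself the quantity being estimated. A source whose patients are there because they were tested cannot show how often prescribers test.

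The selection criterion could favour such a source, one candidate's name suggests that it might be one, and no step in the plan asks how patients enter each cohort. The regulator (CHMP) asked whether prescribers follow the SmPC. An upward bias in this proportion would flatter the answer. It would not shrink with more patients, and the confidence interval would not show it.

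**Working it through.** **1. The plan's own precision figures.** Section 4.1.1 gives 95% half-widths for 400 and 600 patients. With the usual formula, 1.96 × √(p(1−p)/n):

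- p = 0.95, n = 600: 1.96 × √(0.0475/600) = 0.0174, stated as 0.02.
- p = 0.70, n = 600: 1.96 × √(0.21/600) = 0.0367, stated as 0.04.

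All 12 cells of the table reproduce at two decimals. The table is correct, but it covers sampling error only.

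**2. The mechanism, from the text.**

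- Enrolment must precede the start of RPV (Section 3.1.1).
- Suppose that a cohort enrols patients through a resistance test. The test then comes no later than enrolment, and so before RPV.
- As the numerator is worded (Section 4.5.2), that test counts as documented pre-treatment screening. Nearly every RPV patient from that cohort enters the numerator, whatever the prescriber did.

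The supposition in the second step is not in the documents. No enrolment rule is given for any candidate.

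**3. Size, on assumed values.** Let w be the share of RPV patients from a test-defined source, p_R its testing rate and p_0 the rate elsewhere. The documents give none of the three. Then

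pooled = w·p_R + (1−w)·p_0, and shift = w·(p_R − p_0).

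With p_R = 0.98:

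| w | p_0 | Pooled | Shift (points) |
|---|---|---|---|
| 0.20 | 0.70 | 0.196 + 0.560 = 0.756 | 5.6 |
| 0.33 | 0.70 | 0.323 + 0.469 = 0.792 | 9.2 |
| 0.20 | 0.60 | 0.196 + 0.480 = 0.676 | 7.6 |
| 0.33 | 0.60 | 0.323 + 0.402 = 0.725 | 12.5 |

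**4. When the shift reaches the sampling error.** Set w·(p_R − p_0) equal to the half-width at p_0 with n = 600 and solve for w:

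| p_0 | Half-width (points) | w if p_R = 100% | w if p_R = 95% |
|---|---|---|---|
| 60% | 3.9 | 0.10 | 0.11 |
| 70% | 3.7 | 0.12 | 0.15 |
| 80% | 3.2 | 0.16 | 0.21 |
| 90% | 2.4 | 0.24 | 0.48 |

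For example, with p_0 = 80% and p_R = 100%: 0.032/0.20 = 0.16.

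**5. The limits.** If p_R = p_0 the shift is zero at any share. At the other end, Section 2.1 would allow a single cohort (w = 1). If that cohort were test-defined, the pooled figure would equal p_R and would say nothing about prescribing elsewhere.

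**The case against.** The case against is substantial, and much of it stands.

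- **Recording is not testing.** A reader might infer that the study measures screening where testing is most complete. The criterion concerns how finely resistance data are collected, not how often clinicians test, and nothing in the protocol shows that testing is more frequent in such cohorts. Because the numerator is documented screening, a source that records tests poorly would understate it. Good recording is needed here as well as for the mutation outcomes.
- **There is a second criterion.** A reader might take resistance data as the whole basis for selection. Section 1.2 also requires the variables for judging proper use.
- **The resistance database is a candidate only.** It could be rejected as unsuitable at feasibility. That patients enter it through a test is suggested only by its name.
- **The UK linkage is not an instance.** Linking an existing cohort to a resistance database adds test records for people already enrolled. It does not select them on having been tested.
- **Geography helps.** Six of the seven candidates are named for one country, so a summary by geography comes close to a summary by cohort. It would not, however, isolate one source where two cover the same country, and it would not change the pooled figure.
- **Removing a cohort from the primary estimate has a price.** It would break the stated denominator and give the three SmPC proportions different populations. At shares of 20% to 33%, it would leave about 480 to 402 of 600 patients. This is a good reason to leave the primary estimate alone.

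The conditional risk remains. If a test-defined source is selected, the protocol has no stated step that would reveal its effect on this one proportion.

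**Conclusion.** The point holds as a conditional risk, not as a demonstrated bias. The protocol links source selection to resistance data, lists a candidate named for resistance analysis, requires enrolment before treatment, pools the screening proportion over all sources and calls the cohorts generalizable without naming this limitation. If a selected source enrols through a resistance test, the pooled proportion may be too high as a measure of prescriber behaviour.

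A reader might go further and conclude that the proportion is overstated. The documents do not support that, because they give no entry rule, testing rate or share of patients for any cohort. The shifts of 5.6 to 12.5 points rest wholly on assumed values. They show only that a moderate share from such a source could exceed the stated sampling half-widths of 0.02 to 0.04. Those half-widths are correct for what they cover. The other two SmPC proportions are not affected by this mechanism.

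**What to change.** - **Section 4.5.2:** keep the pooled screening proportion over all included RPV starters. Report the same proportion by cohort, and add a sensitivity estimate that leaves out any cohort entered through, or defined by, a resistance test. Cohorts that only link to a resistance database stay in.
- **Section 3.1.3.1:** have the feasibility assessment record how patients enter each cohort, and whether a resistance test is part of entry. This must be known in advance, because with a single test-defined source no sensitivity estimate would be possible.
- **Section 5:** qualify the generalizability statement of Section 2.2 for this proportion.

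The cost is one extra table, a few sentences and a wider interval for the sensitivity estimate. At 70% the half-width would go from 3.7 points with 600 patients to 1.96 × √(0.21/480) = 4.1 points with 480, or 1.96 × √(0.21/402) = 4.5 points with 402. The primary denominator, the mutation outcomes and the other two proportions do not change.
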